### **6.3.3 Endpoints Related to Iron**

These sections address iron-related endpoints from randomization through the end of the trials. The study population will be divided into the following baseline iron groups:

- 0 – those not receiving any iron at baseline,
- I – those receiving only oral iron at baseline,
- II – those receiving only intravenous (IV) iron at baseline, and
- III – those receiving IV and oral iron at baseline.

#### **6.3.3.1 Hepcidin, Ferritin, Total Iron-Binding Capacity, Serum Iron, and Transferrin Saturation**

For hepcidin, ferritin, total iron-binding capacity (TIBC), serum iron, and transferrin saturation (TSAT), the 2 treatment groups will be compared with respect to mean change from baseline and percentage change from baseline in the PEP and SEP. Subgroup analyses and variation with rescue and Hb may be considered.

#### **6.3.3.2 Elemental Iron**

For each baseline iron group and the whole population, a table will present by treatment group the proportion of subjects who received each of the relevant routes and the mean weekly dose of elemental iron. The calculation of mean weekly dose will include subjects with iron administration and will count only weeks in which a subject was still being followed in the denominator.

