4.3 Potential Benefits and Risks

Please see the vadadustat Investigator's Brochure for additional discussion and information for the following section.

Trials of injectable erythropoiesis-stimulating agents (ESAs) in patients with anemia secondary to NDD-CKD or DD-CKD have demonstrated an increased risk of cardiovascular events associated with higher Hb targets (Besarab 1998; Singh 2006; Pfeffer 2009). Post-hoc analyses performed by the FDA and others have shown an association between these adverse outcomes and supraphysiologic serum EPO levels and/or Hb oscillations and overshoots (McCullough 2013, Unger 2010). In studies to date, oral vadadustat daily increased mean Hb with few excursions above the target range. In addition, serum EPO levels remained well below those

reported with ESAs in the literature. As a result, there is the potential for the investigational drug vadadustat to provide an effective and safe therapeutic option for the treatment of renal anemia.

In addition, vadadustat may enhance iron metabolism and transport. Phase 1 and Phase 2 trials have demonstrated a consistent dose-dependent increase in TIBC and decrease in ferritin and hepcidin. Mechanistic studies have demonstrated that HIF stabilization downregulates the iron absorption regulator hepcidin, and upregulates the iron-mobilizing regulators ferroportin and transferrin (and its receptor) (Peyssonaux et al. 2007). Potential clinical benefits include enhanced erythropoiesis and decreased exogenous iron requirements.

The toxicological profile of vadadustat supports continued development in the ongoing Phase 3 clinical trials. Dose-limiting toxicity noted in the exploratory toxicology studies was due to hemoglobinuric nephropathy (rat) and emesis associated with body weight loss (dog). Dose-limiting toxicity noted in the sub-chronic and chronic toxicology studies was due to exaggerated pharmacology and the sequelae of events related to polycythemia (increased RBC mass, blood hyperviscosity and fibrin thrombi); polycythemia-related toxicity was consistent across species, monitorable and reversible. In the completed clinical studies, vadadustat has had an acceptable safety profile to support further development.

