5.3 Secondary Efficacy Endpoints

The key secondary efficacy endpoints include the following:

- Mean change in Hb value between Baseline (mean pretreatment Hb) and the secondary evaluation period (Weeks 40-52)
- Proportion of subjects with Hb values within the target range during the primary evaluation period (Weeks 24-36)
- Proportion of subjects with Hb values within the target range during the secondary evaluation period (Weeks 40-52)

Other secondary efficacy endpoints include:

- Proportion of time with Hb values within the target range during the primary evaluation period (Weeks 24-36)
- Proportion of time with Hb values within the target range during the secondary evaluation period (Weeks 40-52)
- Proportion of subjects with Hb increase of >1.0 g/dL from Baseline

- Time to achieve Hb increase of >1.0 g/dL from Baseline
- Mean change in Hb between Baseline (mean pretreatment Hb) and the primary evaluation period (mean Hb from Weeks 24-36) stratified by pre-baseline ESA exposure
- Progression of CKD
- Proportion of subjects receiving IV iron therapy from Baseline visit to Week 52
- Mean monthly dose of IV elemental iron administered from Baseline to Week 52 in subjects who have received IV iron
- Proportion of subjects receiving RBC transfusion(s) from Baseline to Week 52
- ESA rescue
- Dose adjustments from Baseline to Week 52
-

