**Table 3. Other Efficacy Endpoints**

| Endpoint  | Approach to Analysis   | Comments   |
|---|--|--|
| Hb endpoints – Section 6.3.2  |  |  |
| Change in average Hb value between Baseline and the combined primary efficacy period (PEP) and secondary efficacy periods (SEP) (Weeks 24-52) | Analysis of covariance (ANCOVA) stratified by baseline strata. | Average may include imputed values for PEP and/or SEP.   |
| Having Hb values in the geography-specific target range during PEP or SEP (2 alternate definitions)   | Mantel-Haenszel test stratified by the baseline strata         | This analysis includes the observed hemoglobin values.   |
| CI-0014 only: Hb increase of >1.0 g/dL from Baseline to any time before Week 52   | Mantel-Haenszel test stratified by baseline strata             | This analysis includes the observed hemoglobin values.   |
| CI-0014 only: Time to achieve Hb increase of >1.0 g/dL from Baseline Hb (censored at Week 52)   | Time – to – event  | This analysis will use only observed data.   |
| Progression of CKD ( Section 6.3.6 )  |  |  |
| Progression of CKD (entire length of study)   | Time – to – event  |  |
| Iron endpoints ( Section 6.3.3 )  |  |  |
| Receipt of at least 1 administration of elemental iron ( IV, or oral)   | Mantel-Haenszel test stratified by baseline strata             |  |
| Average weekly dose of elemental iron, IV, or oral  | ANCOVA stratified by baseline strata.                          | If the distribution is highly skewed either because of a large spike at zero or a long tail to the right (or both), other methods may be considered. |

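### The weekly iron dose is defined in post-randomization iron receivers only, and the planned between-arm ANCOVA names no other set, so it may not be a randomized comparison

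*SAP*

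**What the plan says.** SAP 6.3.3 sets the time frame: "These sections address iron-related endpoints from randomization through the end of the trials". Section 6.3.3.2 then plans a table by treatment group, for each baseline iron group and for the whole population, giving "the proportion of subjects who received each of the relevant routes and the mean weekly dose of elemental iron". On the dose it states: "The calculation of mean weekly dose will include subjects with iron administration"; it adds that the calculation "will count only weeks in which a subject was still being followed in the denominator".

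Table 3 lists average weekly dose of elemental iron under a header that points back to Section 6.3.3. It assigns an ANCOVA stratified by the baseline strata and allows other methods "If the distribution is highly skewed either because of a large spike at zero or a long tail to the right". Receipt of iron has its own row, with a stratified Mantel-Haenszel test. Appendix C.1.4 models the dose by route (oral, IV) for each Year 1 period and for Week 52 to end of study, and does not say which subjects enter.

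The current protocol carries a similar restriction for IV iron. Protocol 5.3 lists "Mean monthly dose of IV elemental iron administered from Baseline to Week 52 in subjects who have received IV iron", next to the proportion receiving IV iron. Protocol 4.3 names "decreased exogenous iron requirements" among the potential clinical benefits of vadadustat.

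**The concern.** Whether a subject receives iron in the study is decided after randomization and may depend on the assigned drug. Iron is prescribed against ferritin and TSAT (Protocol 8.4.6). Protocol 4.3 reports that vadadustat lowers ferritin and raises TIBC, and treatment is open-label. If the drug changes who is given iron, the receivers in the two arms are differently selected patients, and the difference in their mean dose mixes a drug effect with a selection effect. The baseline iron groups do not remove this, because later receipt still selects subjects within each group.

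If vadadustat spared iron mainly in milder cases, the remaining receivers would be the heavier users, and their mean could rise while total iron use falls. A reader could then take from the dose comparison that vadadustat raises iron need when randomized subjects as a whole used less.

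**Working it through.** The plan states no power, effect size or expected iron use for this endpoint, so there is no figure to reproduce. The check is algebra, followed by illustrations on assumed inputs.

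**Condition for a sign reversal.** Let p be the proportion receiving iron and m the mean weekly dose among receivers, with V for vadadustat and D for darbepoetin alfa. If each subject's dose is averaged over that subject's own followed weeks, with zero for those given none, the all-subject mean is p × m.

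- Receivers-only difference above zero: mV > mD, that is mV/mD > 1.
- All-subject difference below zero: pV × mV < pD × mD, that is mV/mD < pD/pV.
- Both together: **1 < mV/mD < pD/pV**.

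The condition depends on the proportions only through their ratio. If receipt on vadadustat is 0.9, 0.8 or 0.6 times that on darbepoetin alfa, the upper limit is 1/0.9 = 1.11, 1/0.8 = 1.25 or 1/0.6 = 1.67.

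**Illustrations (all inputs assumed).**

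| Vadadustat | Darbepoetin alfa | Receivers only (mg/week) | All subjects (mg/week) |
|---|---|---|---|
| 30% at 60 | 40% at 50 | 60 − 50 = +10 | 18 − 20 = −2 |
| 35% at 60 | 50% at 50 | 60 − 50 = +10 | 21 − 25 = −4 |
| 20% at 70 | 40% at 60 | 70 − 60 = +10 | 14 − 24 = −10 |

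**Simulation (distributions assumed).** Each subject has a latent iron need, and no subject would receive more iron on vadadustat than on darbepoetin alfa.

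- Lognormal need (median 40 mg/week, log-SD 1.0), with vadadustat only raising the need at which iron starts from 20 to 35. Receipt is 75.6% on darbepoetin alfa and 55.3% on vadadustat. The all-subject means are 63.0 and 57.5 (−5.5). The receivers-only means are 83.3 and 103.9 (+20.6).
- In 4000 simulated trials of 925 per arm under that model, a two-sided Welch t-test at 0.05 among receivers is significant in the wrong direction in 96%. This falls to 72% if the starting need rises only to 30, and to 25% if only to 25. The all-subject test is significant in the correct direction in 28%, 14% and 6% of trials respectively.
- If instead vadadustat lowers each dose by a fixed amount, to no less than zero, reversal is not general. Exponential need gives a receivers-only difference of 0.0 against −8.7 over all subjects. Uniform need gives −7.5 against −10.9, which is the correct sign.

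**Which set does the ANCOVA use?** Section 6.3.3.2 gives the only definition of the dose. Table 3 refers to Section 6.3.3, and neither Table 3 nor C.1.4 replaces that definition. The phrase "either because of a large spike at zero" in Table 3 would fit an all-subject variable. It would also fit a receivers-only one: a subject given only oral iron has zero IV dose, and a subject given iron in one period may have none in another. The set is therefore unsettled, and programmers could build different variables from the same text.

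**The case against.** The strongest reply is that the restricting sentence sits in the description of a summary table with no test attached, while the between-arm analysis is in Table 3 and C.1.4, neither of which limits itself to receivers. If Table 3 intends zeros, the plan already has an all-subject ANCOVA and a receivers-only descriptive row. This stands only in part. Table 3 points back to Section 6.3.3 for the endpoint, and nothing supplies another set, so the intended reading cannot be confirmed.

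A reader might infer that Table 3 contradicts 6.3.3.2, because zeros seem to require non-receivers. The documents do not support that: zeros can arise among receivers by route or by period.

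A reader might also infer that the protocol predicts less iron use on vadadustat. Protocol 4.3 lists this only as a potential benefit.

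Three further limits stand in full. The proportion receiving each route appears beside the dose, and receipt has its own stratified analysis, so a careful reader can multiply the two. SAP 9.3 calls these endpoints exploratory, and C.1.3 makes continuous endpoints beyond the two formally tested Hb changes descriptive. The magnitudes are all assumed, and the model with the high wrong-direction rates lets treatment act only by raising the need at which iron starts in one arm, whereas the protocol states one iron target for both arms.

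**Conclusion.** The point holds in a limited form. As written, the plan can compare mean iron dose between post-randomization subsets, and that contrast does not estimate the effect of assignment on iron use. Its sign can be opposite to the all-subject difference when the receivers' mean-dose ratio (vadadustat to darbepoetin alfa) lies between 1 and the ratio of receipt proportions (darbepoetin alfa to vadadustat). It need not be: some assumed mechanisms give no difference or the correct sign. No size can be given from the documents, because they contain no iron-use proportions or doses.

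It would go too far to say that the comparison will mislead, or that the planned ANCOVA is certainly restricted to receivers. The primary, key secondary and MACE conclusions are not touched. What is at risk is the reading of an exploratory estimate of iron use. That justifies a change because the change costs little.

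**What to change.** State the same analysis set in SAP 6.3.3.2, Table 3 and Appendix C.1.4. Define the between-arm comparison as average weekly elemental iron, by route, in all randomized subjects followed in the period. Count zero for subjects given none, and keep the existing denominator of weeks in follow-up. Table 3's allowance for other methods under skewness can remain.

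Keep the receivers-only mean as a row labelled descriptive and conditional on receiving iron, beside the proportion receiving it. For IV iron from Baseline to Week 52, expressed per month, that row also serves the protocol's endpoint.

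The cost is SAP wording in three places and one derived variable, with no new data. The gain is a comparison that keeps the randomized groups; the simulation gives no reason to expect high power from it.

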### **6.3.4 Other Laboratory Parameters**

The following efficacy endpoints are related to laboratory chemistry:

- Change in serum glucose between Baseline and the PEP (Weeks 24 to 36).
- Change in lipid parameters between Baseline and the PEP (Weeks 24 to 36) – including total cholesterol, low-density lipoprotein (LDL) cholesterol, high-density lipoprotein (HDL) cholesterol, and triglycerides.

### 6.3.5 Dose Adjustments and Interruptions

An important aspect of evaluating the efficacy of vadadustat arm is to understand how often dose adjustments are needed to maintain target Hb levels. To that end, the pattern of dose changes in the 2 treatment arms will be described, including percent with dose adjustment or treatment interruption for the whole study and by the four analysis time periods in Year 1 (see [Section 5.1](#)).

### 6.3.6 Progression of CKD

Progression of chronic kidney disease (CKD) in both studies is defined as experiencing any of the following:

- Transition to chronic dialysis, or
- Receipt of a kidney transplant, or
- Estimated glomerular filtration rate (eGFR) <15 mL/min per 1.73 m^2 and confirmed by another measurement with a reduction of eGFR <15 mL/min per 1.73 m^2, which should be at least 28 days apart from the first reduction, or
- Reduction in eGFR of 40% or more from baseline (confirmed by second measurement at least 28 days later).
- The endpoint for analysis is time to progression of CKD. See [Coresh, 2019](#); [Heerspink, 2019](#); [Levey, 2014](#) for a description of the endpoint.

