7.2 Inclusion Criteria

Subjects must meet all of the following inclusion criteria to be eligible:

1. At least 18 years of age
2. Diagnosis of CKD with an estimated glomerular filtration rate (eGFR) ≤ 60 mL/min/1.73 m² using the 2009 Chronic Kidney Disease Epidemiology Collaboration (CKD-EPI) creatinine equation during Screening (see [Appendix B: CKD-EPI Creatinine Equation](#)) and not expected to start dialysis within 6 months of Screening

3. Currently maintained on ESA therapy with a dose received within 6 weeks prior to or during Screening
4. Mean Screening Hb between 8.0 and 11.0 g/dL (inclusive) in the US and between 9.0 and 12.0 g/dL (inclusive) outside of the US, as determined by the average of 2 Hb values measured by the central laboratory during Screening
5. Serum ferritin ≥ 100 ng /mL and TSAT $\geq 20\%$ during Screening
6. Folate and vitamin B₁₂ measurements \geq lower limit of normal (LLN) during Screening
7. Understands the procedures and requirements of the study and provides written informed consent and authorization for protected health information disclosure.

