Refer to [Sections 7.4.1, Retesting](#) and [7.4.2, Rescreening](#) for further details regarding repeating laboratory measurements during the Screening period.

- **Point of care Hb:** Using HemoCue, Hb will be monitored throughout the study to determine if the dose of study medication (vadadustat or darbepoetin alfa) will be

adjusted, interrupted, or maintained as described in [Section 8.4.4 Dosing and Dose Adjustment Guidelines](#).

- Reticulocyte count: An automated reticulocyte count (both absolute and percent) will be performed at Baseline and at Weeks 4, 12, 28, and 52.
- Coagulation tests: Blood samples will be drawn at Baseline to assess the prothrombin time (PT), partial thromboplastin time (PTT), and international normalized ratio (INR).
- Folate and Vitamin B₁₂: A blood sample will be drawn at SV1 to assess the folate and Vitamin B₁₂ levels.
- Urine albumin-to-creatinine ratio (uACR): A random urine spot sample should be collected at the investigative site during the Baseline, Weeks 28, 52, 104, 156, 208, and EOT to assess the uACR. Subjects should refrain from heavy exercise 24 hours before the test.
- C-reactive protein (CRP): A blood sample for CRP will be collected at the Baseline, Weeks 28, 52, 104, 156, and EOT.
- Serum Chemistry: Blood samples to assess serum chemistry will be collected at SV1, Baseline, and twice annually at Weeks 28, 52, 76, 104, 128, 156, 180, 208, EOT. At all other noted visits in [Appendix A: Schedule of Activities](#), serum creatinine and eGFR will be performed only at Weeks 4, 8, 12, 20, 36, 44. The serum chemistry will include the following assays: sodium, potassium, bicarbonate, chloride, calcium, magnesium, phosphorus, glucose, creatinine, blood urea nitrogen (BUN), creatine phosphokinase (CPK), uric acid, albumin, total protein, and eGFR calculation.
Note: When a $\geq 50\%$ decline in eGFR from the Baseline value is observed, a repeat central laboratory measure should be performed within 30 to 60 days.
- Liver Function Tests: Blood samples to assess liver function will be collected at SV1, Baseline, Weeks 4, 8, 12, 16, 20, 24, 28, 36, 44, 52, 64, 76, 88, 104, 116, 128, 140, 156, 168, 180, 192, 208, and EOT. Liver function tests will include: total bilirubin, alkaline phosphatase, ALT/SGPT, AST/SGOT, and lactate dehydrogenase (LDH).

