### *Study CI-0015*

- Conversion and Maintenance Period (Weeks 0-52):
  - Weeks 0 to 23: conversion to study treatment for maintaining Hb
  - Weeks 24 to 36: PEP
  - Weeks 40 to 52: SEP

After Week 52, subjects in both studies will proceed to the following 2 periods:

- **Long-Term Treatment Period (Weeks 53-End of Treatment [EOT]):** continued treatment with study medication to assess long-term safety
- **Follow-up Period (EOT + 4 weeks):** post-treatment visit (either in person or by telephone) to assess safety

The duration of the trial will depend on how long it takes for a total of 631 adjudicated MACE to occur in the 2 studies combined. A separate SAP will describe the planned MACE analyses, including the method planned for pooling data from the 2 PRO2TECT studies.

The safety reporting period for a subject enrolled in this study begins upon randomization and ends at the final protocol-required study contact (visit or telephone), also known as a subject's end of study (EOS). In addition, the Investigator should report any adverse event (AE) that occurs after this period if he or she assesses it as possibly or probably related to the study medication.

According to the schedule of visits in the protocol, no laboratory assessments, physical exams, or other procedures are planned after the subject's permanent discontinuation of study medication, also known as EOT; however, AE and rescue therapy assessments, including monitoring for MACE endpoints, will continue until a subject's EOS.

The analysis time periods for efficacy divide the Correction/Conversion and Maintenance periods, Year 1 collectively, into four windows (see [Table 1](#)).

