## 5.2 Definition of Baseline

In general, the baseline value will also be the value of assessment closest to the end of the window, i.e., Day 1 (first dose date). The baseline value must be assessed prior to initiation of study treatment. In contrast, the baseline value for laboratory-based efficacy outcomes (e.g., Hb, ferritin, hepcidin, TSAT, serum iron, TIBC, and lipids) will be an average of the last 1 or 2 values prior to or on the first dose date, as specified in [Section 9.1.1](#).

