## Statistical Analysis Plan AKB-6548-CI-0014 and AKB-6548-CI-0015

- Hypertension
  - No Hypertension
  - Hypertension
  - Medications (CI-0015 only)
- Baseline ESA dose (See Locatelli, 2004 for justification of the choice of cut-off values)
  - $\leq 90$  U/kg/week
  - $>90$  and  $<300$  U/kg/week
  - $\geq 300$  U/kg/week

*Baseline laboratory measurements*

- Urine albumin-to-creatinine ratio (uACR) – reference for cutoff: Gansevoort, 2011.
  - $<300$  g/kg
  - $\geq 300$  g/kg
- Estimated GFR – The threshold of 15 represents a value between CKD eGFR stages 4 and 5
  - $<15$  mL/min/1.73m^2
  - $\geq 15$  mL/min/1.73m^2
- C-reactive protein. In Q2 laboratories, which are the labs used in these studies, the normal range is 0 to 0.6 mg/dL.
  - $\leq 0.6$  mg/dL
  - $>0.6$  mg/dL
- Baseline TSAT
  - $<$  median of Baseline TSAT (%)
  - $\geq$  median of Baseline TSAT (%)
- Baseline ferritin
  - $<$  median of baseline ferritin (ng/mL)
  - $\geq$  median of baseline ferritin (ng/mL)

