## D.3. Analysis of Time to Event Data

This section describes the methods for analyzing time-to-event endpoints, for example, time to:

- achieve 1g/dL increase in Hb in Year 1 (CI-0014)
- first rescue therapy (by series of definitions)
- first RBC transfusion
- first ESA use (aside from control arm medication not specified as rescue)
- progression of chronic kidney disease (CKD).
- study discontinuation

Time-to-event distributions will be estimated using the Kaplan-Meier product-limit method and log rank test.

The hazard ratio and corresponding 95% confidence interval for the comparison of vadadustat to darbepoetin alfa will be estimated using a Cox proportional hazards model, with treatment group and other predictors as covariates. Analyses in the randomized population will be stratified by the stratification factors; analyses in subgroups will be conducted similarly. The predictor variables (&PREDVAR. in [Exhibit D 3](#)) for hemoglobin-related events are baseline ESA dose (three

Statistical Analysis Plan AKB-6548-CI-0014 and AKB-6548-CI-0015

levels specified in [Section 11](#)) and continuous baseline Hb. For CKD progression, the predictor variable is continuous baseline eGFR.

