  - < median of CI-0016 and CI-0017 combined
  - $\geq$  median of CI-0016 and CI-0017 combined
- Incident Dialysis Patients
  - CI-0016 and CI-0017
    - All patients in CI-0016 plus patients who have  $\leq 16$  weeks of dialysis history from the date of informed consent in CI-0017
- Pooled analysis of patients with CKD G5 and incident dialysis patients (those who initiated dialysis within 16 weeks) after all studies indicated below are completed
  - <15 ml/min/1.73m^2 (CKD Stage 5) at baseline from CI-0014 and CI-0015
  - All patients in CI-0016 plus patients who have  $\leq 16$  weeks of dialysis history from the date of informed consent in CI-0017

In these summary statistics, only the primary analysis method will be presented. Hazard ratios and their 95% confidence intervals for subgroups will be displayed using forest plots.

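### The CKD progression endpoint counts a confirmed eGFR below 15 with no baseline condition, so most subjects already below 15 at entry become early progressors without any change, and a true hazard ratio other than 1 is pulled towards 1

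*SAP*

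**What the plan says.** SAP 6.3.6 defines progression as the first of four events: chronic dialysis, kidney transplant, eGFR below 15, or a fall of at least 40% from baseline. The two eGFR components need confirmation at least 28 days later. The below-15 component reads "and confirmed by another measurement with a reduction of eGFR <15 mL/min per 1.73" m²; it names no baseline value, whereas the 40% component beside it is explicitly measured from baseline.

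Protocol 7.2 requires eGFR at or below 60 and sets no lower limit. The only restriction at the low end is "and not expected to start dialysis within 6 months of Screening". Subjects below 15 are clearly expected. SAP 11 sets baseline subgroups below 15 and at or above 15 ("The threshold of 15 represents a value between CKD eGFR stages 4 and 5"), and MACE SAP 5.1 plans a pooled analysis whose first group reads "CKD Stage 5) at baseline from CI-0014 and CI-0015".

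eGFR is measured often and early. Protocol 9.2.2 states "serum creatinine and eGFR will be performed only at Weeks 4, 8, 12, 20, 36, 44" outside the full chemistry visits, which in Year 1 are Weeks 28 and 52.

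The analysis is a Cox model for time to progression (SAP Table 3 and Appendix D.3): "For CKD progression, the predictor variable is continuous baseline eGFR". The current protocol lists the endpoint in 5.3 without defining it, so SAP 6.3.6 is the only operative definition, for both CI-0014 and CI-0015.

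**The concern.** A subject who enters with eGFR 12 and stays at 12 satisfies the rule at the first post-baseline visits. Nothing has progressed, yet the subject is an event. Any later dialysis, transplant or 40% decline can then no longer be the first event and drops out of the comparison.

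Such events arise at about the same rate in both arms. They inflate reported incidence and dilute whatever real difference exists, so a renal harm and a renal benefit would both be understated. This composite is the only planned time-to-event renal comparison in SAP Table 3. The SAP also does not say whether an eGFR event is dated at the first or the confirming value.

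**Working it through.** The documents give no event rate, sample size or power for this endpoint, so there is no planned figure to reproduce. The check asks how often unchanged subjects qualify, and what that does to the hazard ratio.

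**Step 1: unchanged subjects who qualify.** Take observed eGFR = true value e × exp(CV × Z), with Z standard normal. One value falls below 15 with probability p = Φ(ln(15/e)/CV). If the next value must confirm, and visit windows are ignored, the chance of an event from Weeks 4, 8 and 12 is p² + (1 − p)p² = p²(2 − p). At CV 10%:

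- e = 13: p = Φ(0.1431/0.10) = 0.924, giving 0.853 × 1.076 = 0.92.
- e = 14.5: p = Φ(0.0339/0.10) = 0.633, giving 0.400 × 1.367 = 0.55.

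The population version was simulated, with about 300,000 subjects per cell. Assumptions: true eGFR lognormal (log-SD 0.45, range 8–70, median 18 or 25), no true change, and CV 5, 10 or 15%. From the documents: visit weeks and windows, entry at or below 60, and baseline as one measured value (SAP 5.2: "In general, the baseline value will also be the value of assessment closest to the end of the window"). Among stable subjects with measured baseline below 15, the share counted is:

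| By | CV 5% | CV 10% | CV 15% |
|---|---|---|---|
| Week 12 | 86–90% | 73–80% | 62–72% |
| Week 28 | 92–94% | 83–88% | 75–83% |

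For measured baselines of 13.5–15 the Week 12 figure is 36–69%. If any later value may confirm, the upper ends in the table become 91% and 96%.

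**Step 2: effect on the hazard ratio.** From the documents: 925 per arm (SAP 2.6), and 20 months' accrual with up to 36 months' follow-up (MACE SAP 2.5.1), so follow-up is uniform from 36 − 20 = 16 to 36 months. Assumed: a real progression hazard of λ × 2^((25 − e)/10), with λ = 0.25 or 0.10 per year. The Cox model has treatment and measured baseline eGFR; the event is dated at the first value; there are 300 replicates per scenario (Monte Carlo SE at most 0.006 on the log scale). Estimated hazard ratio as written, range over the three CVs, by assumed share below 15:

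| True HR, λ | 10% | 20% | 30% | 40% |
|---|---|---|---|---|
| 1.25, 0.25 | 1.19–1.20 | 1.15–1.16 | 1.12–1.13 | 1.10–1.11 |
| 1.25, 0.10 | 1.14–1.16 | 1.10–1.11 | 1.07–1.09 | 1.05–1.07 |
| 0.80, 0.25 | 0.85 | 0.87–0.88 | 0.89–0.90 | 0.91–0.92 |
| 0.80, 0.10 | 0.88–0.89 | 0.91–0.92 | 0.93–0.94 | 0.94–0.96 |

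A true ratio of 1.00 stays at 0.996–1.005 (CV 10%).

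The mechanism shows in the event counts. At a 20% share, CV 10% and true 1.25, threshold events in subjects already below 15 make up 309 of 1040 (30%) at λ = 0.25 and 329 of 733 (45%) at λ = 0.10. A crude event-weighted average gives exp(0.703 × ln 1.25) = 1.17 and exp(0.551 × ln 1.25) = 1.13. The simulated 1.150 and 1.107 are lower because noise crossings from subjects at or above 15 also carry no treatment effect. Real events alone give 1.24–1.26.

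**Step 3: variations on that 20% case.** Dating at the confirming value gives 1.155 and 1.109. SAP 2.2 says "no laboratory assessments, physical exams, or other procedures are planned after the" end of treatment; stopping eGFR there, with 20–40% a year discontinuing, gives 1.154–1.168 and 1.104–1.114.

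A second simulation used other assumptions: log-SD 0.55, mean follow-up 1.8 years, and a hazard of 0.2 per year scaled by 20/eGFR. With 4, 11, 18 and 30% below 15, a true 0.75 becomes 0.81, 0.86, 0.88 and 0.94, and a true 1.25 becomes 1.19, 1.14, 1.12 and 1.09. Hazard ratios with and without baseline eGFR differed by 0.03 or less.

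**The case against.** The best textual argument is that the bullet twice uses the word reduction, so a programmer might require a fall to below 15. The section also points to three publications for a description of the endpoint, and these were not available. The word does hint at that intent, but it gives neither a starting level nor a size of fall. An analysis definition should not depend on a programmer's guess or on outside papers.

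Other safeguards do not close the gap. Baseline eGFR as a covariate cannot help, because the extra events are uninformative about treatment at any baseline level. The Appendix D.3 censoring rule concerns subjects without an event. That appendix says subgroup analyses will be done similarly, and a subgroup at or above 15 would remove these events. However, SAP 11 commits the eGFR subgroups only for the primary and secondary endpoints. SAP 1 lets a blinded team settle unforeseen conventions, but does not commit it to this one.

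SAP E.1.5 tabulates falls of at least 40%, and transition to dialysis is reported as a serious adverse event. For transplant, Protocol 10.1.1 says in one place that it is not recorded as an adverse event and in another that it is reported as serious; those passages need reconciling. These tables are descriptive and do not repair the composite.

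What stands is the limit on size. The share below 15, progression rate and CV are all assumed. The simulation gives threshold events in unchanged subjects no treatment effect, which is what unchanged means, but the dilution follows from it. At a 10% share and λ = 0.25 the shift is about 0.05 on the log scale against a standard error of 0.07. SAP 9.3 treats the endpoint as exploratory, without multiplicity control.

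**Conclusion.** The concern holds. As written, the rule counts most subjects who enter below 15 as progressors within the first months, and it moves any true hazard ratio other than 1 towards 1. The direction was the same in every non-null scenario. The size depends mainly on the share below 15 and on how common real progression is: for a true 1.25, the estimate runs from about 1.20 (10% share, λ = 0.25) to 1.05 (40% share, λ = 0.10). Under a true ratio of 1 there is no shift in the estimate, but incidence is still inflated. The primary haemoglobin, key secondary haemoglobin and MACE conclusions are untouched, so this should be fixed but does not threaten the trial's main conclusions.

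**What to change.** In SAP 6.3.6, apply the confirmed below-15 component only to subjects whose baseline eGFR is at least 15. Keep dialysis, transplant and the confirmed 40% decline for everyone. Add one sentence fixing whether both confirmed-eGFR components are dated at the first or the confirming value; either works.

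Under the amended rule, a true 1.25 is estimated at 1.21–1.25 (λ = 0.25) or 1.18–1.23 (λ = 0.10), and a true 0.80 at 0.81–0.83 or 0.81–0.85. Recovery is not complete, because measurement noise still carries some stable subjects across the line: 26–51% of those with measured baseline 15–17 by Week 104, and 2–14% of all subjects at or above 15.

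The cost is two sentences before database lock, using data already collected. Reported incidence will fall, because events in subjects already below 15 are no longer counted.
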